2.2 Patient EMR data

All patient data is saved in the EMR. At various points, this data is collated into SOAP notes (structured text files describing subjective and objective signs and symptoms, the provider's assessment (diagnosis), and the treatment plan).

The SOAP notes that are saved are:

- “Unassisted” SOAP note created on initial patient consultation and submitted to LLM: contains care plan conditional on results of requested medical tests, randomly labeled SOAP A or B
- “Assisted” SOAP note created after LLM feedback was received: conditional care plan, randomly labeled B or A
- Conditional MO SOAP note: conditional care plan, created by MO prior to receiving laboratory test results
- Patient discharge SOAP note: patient care plan created by MO after receiving laboratory test results and communicated to patient
- Final MO SOAP note: patient care plan created after reviewing study medical tests (malaria, anemia, UTI).

In addition, we have the values of individual EMR fields that make up these SOAP notes, e.g. test results, diagnoses, prescriptions, etc., including patient demographics and vital signs.

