3.1 Estimation

The primary analysis estimates the effect of LLM assistance on the four outcomes above, all broad indicators for the overall quality of care provided. Every outcome is measured both for assisted and unassisted SOAP notes. We will estimate

$$Y_{it} = a_i + bT_k + cX_{ik} + \epsilon_{ik}$$

where i is the patient (or patient-test combo in 3.5) and $k = \{A, B\}$ is the SOAP note. Y_{ik} is the outcome, a_i is a patient (patient-test) fixed effect, T_k is an indicator for “assisted” and X_{ik} are optional controls for order effects and unblinding (see next section).

We will calculate robust standard errors. In addition, we will separately report p-values using the Benjamini Hochberg procedure for controlling false discovery rates at $p = 0.05$. This will lead to a conservative estimate of the power of our statistical tests. We will also separately report means, standard deviation, and number of observations of each variable for the assisted and unassisted notes.

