3.4 An indicator for the better treatment plan

Based on the DALY rating of SOAP Note A vs. B (counting instances with no errors as 0 DALY loss) we will define an indicator that is 1 if the SOAP Note has the better treatment plan (lower DALY loss). This indicator is 0 for both notes if the notes are judged to be the same according to this question, asked after the MO rated Note A:

Are there any *meaningful* differences in the treatment plans of SOAP Note A and B?

Only if the answer is “yes” or “unsure”, the review of SOAP Note B proceeds.

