5.1 Blinding

We will conduct checks to control for the possibility that imperfect blinding to the intervention (i.e. MO knowledge whether a patient note was “LLM assisted” or not) is impacting our results.

- We measure each MO’s beliefs about whether a given patient note was LLM-assisted with a survey question. We will analyze whether MO beliefs about whether a note was LLM assisted are predicted by true LLM assistance status.
- As a robustness check, we will control for MO beliefs about LLM assistance and for any order effects (i.e. identity of note A vs. B) in the main analysis.
- Ex post, if we find that MOs can reliably predict whether a note was LLM assisted, we will seek to identify whether there are specific outcome-irrelevant features of notes which aid in this prediction, and may run additional robustness checks on a subset of patients where this feature was absent, so blinding is better maintained.

Bias in the difference in evaluation between notes A and B can arise if the MO (i) correctly guesses which note is assisted by the LLM, and (ii) systematically rates notes more highly if they are assisted by the LLM, but *not* due to higher quality of care/true lower harm to the patient.

For the first note that each MO sees (note A), we elicit a “raw” evaluation score prior to seeing note B. This score is then amended into an “adjusted” final evaluation (the reason for the update is the potential for learning about note A, given the cognitively demanding task of the MO: for example, only when shown the highlighted differences between the two notes may the MO detect an error in note A.) In an ideal world, the “adjusted” rating simply reflects the MO’s evaluation given full information. This is the measure we use in most of our analysis. However, the “raw” score provides an opportunity for another blinding check, under the assumption that blinding is more problematic for note B than note A.

If this is the case, a cleaner but noisier estimate of our main effect can be obtained by using an across-patient comparison of the “raw” scores of assisted and unassisted SOAP notes A. This regression will be identical to our baseline specification, but omitting the patient fixed effects.

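### The raw Note A comparison drops the patient fixed effects and names no baseline covariates in their place, so an unbiased but noisy blinding check is somewhat less precise than it could be

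*SAP*

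**What the plan says.** Section 3.1 regresses each outcome on a patient fixed effect, an assisted-note indicator and covariates X that "are optional controls for order effects and unblinding (see next section", the bracket pointing forward to the blinding checks. It names no other covariates.

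Section 5.1 explains that, for the first note each MO reads, "we elicit a “raw” evaluation score prior to seeing note B". If blinding is weaker for Note B than for Note A, the SAP expects that comparing these raw scores across patients gives "a cleaner but noisier estimate of our main effect". Of that regression it says: "This regression will be identical to our baseline specification, but omitting the patient fixed effects".

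Section 2.2 states that the A and B labels are assigned at random and that the EMR fields are held, "including patient demographics and vital signs". Section 2.3.1 uses separate harm scales for patients under 18 and for adults. Section 4.3 expects the scope for harm to depend on how ill the patient is.

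**The concern.** With one note per patient, the patient effects have to go. Once they are gone, the variation between patients, raters and harm scales all enters the residual. In a sample of Note A only, the order control is a constant and drops out. The only term left from X is the MO's belief about assistance, which serves the unblinding question and is not a baseline covariate.

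The SAP's own text suggests that age group and illness severity affect the ratings. Adjusting for variables fixed before Note A is rated would not disturb a randomised comparison. A wider interval makes it harder to tell whether this check agrees with the main analysis, and that comparison is its purpose.

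**Working it through.** The SAP gives no power or precision figure, outcome rate, covariate R² or within-patient correlation ρ, so there is nothing to reproduce. **Inputs from the SAP:** about 500 patients, 20 CHEWs and two clinics (Section 2.1); MO-rated data from before 2/25 excluded, number not given (Section 5.4). **Assumed:** a 1:1 split of Note A, outcome rate 0.5, ρ of 0.3 to 0.8, four MOs, two-sided 5% level, 80% power.

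**1. Unadjusted check.** SE = √(4·p(1−p)/N) = √(4 × 0.25/500) = 0.0447. Detectable difference = (1.960 + 0.842) × 0.0447 = 0.125. At N = 300 these are 0.0577 and 0.162.

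**2. Cost of losing the pairing.** The within-patient variance is 2·p(1−p)(1−ρ)/N, so the SE ratio of across-patient to within-patient is √(2/(1−ρ)): 1.69 at ρ = 0.3, 2.00 at 0.5, 2.58 at 0.7 and 3.16 at 0.8.

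**3. Gain from a short covariate set.** Simulation under assumed inputs, with MO effects, an adult/child term and one baseline covariate, gave a 3-8% smaller SE for any treatment error when these are prognostic. A rough hand check agrees. Let the MO effects and one patient covariate each have SD s on the probability scale. With four MOs, the expected variance explained is s² + ¾s² = 1.75s².

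| s | R² = 1.75s²/0.25 | SE factor √(1−R²) | Reduction |
|---|---|---|---|
| 0.10 | 0.070 | 0.964 | 3.6% |
| 0.15 | 0.158 | 0.918 | 8.2% |

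A 3-8% smaller SE lowers the detectable difference at N = 500 from 0.125 to between 0.125 × 0.97 = 0.121 and 0.125 × 0.92 = 0.115. It is worth 1/0.97² = 1.06 to 1/0.92² = 1.18 times the patients. At ρ = 0.5 the ratio in step 2 falls from 2.00 to 1.94 or 1.84, so 6-16% of the excess over the paired SE is recovered.

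**4. Cost if the covariates are not prognostic.** The SE rises by roughly 1/√(1−k/N) for k added terms. MO effects (3), scale, age and sex make k = 6: 1/√(1−6/500) = 1.006 at N = 500 and 1/√(1−6/300) = 1.010 at N = 300.

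**5. Why the list should be short.** With 19 CHEW terms, 3 MO terms and one covariate, k = 23 and the formula gives 1/√(1−23/500) = 1.024. A simulation with no prognostic effects gave the same: 0.0464/0.0453 = 1.024. With those effects truly prognostic, the SE fell from 0.0435 to 0.0415 (moderate) or from 0.0445 to 0.0398 (larger), and power for a 10-point difference rose from 61% to 64% or from 56% to 65%. The mean estimates with and without adjustment differed by no more than 0.001 in each setting, so the issue is precision and not bias.

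**6. Severe errors.** Section 3.3 sets the cutoff at the 95th percentile of harm in unassisted notes. With about 250 unassisted Note As and a share near 5%, that is 250 × 0.05 = 12.5, or about 12 events. A long list of 19 CHEW, 3 MO, one scale and six patient terms has k = 29. Simulated, it raised the SE by about 3% at N = 500 and 2-6% at N = 300, even when some of the covariates were prognostic.

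**7. Scope.** Section 3.1 covers all four outcomes: "The primary analysis estimates the effect of LLM assistance on the four outcomes above". Outcome 3 (Section 3.4) is built from the ratings of both notes, whereas the raw score precedes sight of Note B. Outcome 4 (Section 3.5) comes from screening tests and treatment guidelines. Neither has a raw Note A score.

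**The case against.** The strongest reply is that the SAP makes no error here. It discloses that the estimate is noisier, the note order is random once the data before 2/25 are set aside, and an unadjusted comparison is valid. Covariates in a robustness check could be called a matter of taste, their R² is not in the SAP, and a long list can do harm. Much of this stands. It limits the point to efficiency, and it rules out CHEW effects and the full set of vital signs. It does not remove the point: a short set offers a modest gain at almost no risk and is easy to fix in advance.

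A reader might infer more, and the document does not support it:

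- *That the check is biased or unusable.* It is neither, and covariates would not turn it into a precise check, because the pairing accounts for most of the lost precision.
- *That this is the only estimate unaffected by sight of the other note.* Outcome 4 does not use the MO's ratings of either note, and Section 5.1 lists other blinding checks.
- *That calling the regression identical to baseline makes the plan contradictory for outcome 3.* Section 5.1 confines the comparison to raw Note A scores, so no analyst would try to run it for outcome 3. Only a statement of scope is missing.
- *That adjustment is worth 25% or 43% more patients.* Those figures need an R² of 0.2 or 0.3, for which the SAP gives no basis.

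**Conclusion.** The point holds as a minor improvement in efficiency. The raw Note A regression is left without baseline covariates, and a short prespecified set would make it somewhat more precise: about 3-8% smaller SE for any treatment error if the covariates are prognostic, and about 1% loss or less if they are not. These sizes rest on assumed rates, effect sizes and number of MOs. For severe errors no gain should be expected from more than a scale indicator. The main analysis and the validity of the check are untouched.

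**What to change.** In Section 5.1, replace the sentence on the specification with one that does the following:

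- For any treatment error and average DALY, regress the raw Note A outcome on the assisted indicator with MO effects, an adult/child scale indicator, patient age and patient sex, all fixed before Note A is rated. Report the unadjusted estimate alongside.
- For severe errors, keep the unadjusted estimate or add only the scale indicator.
- State that the check covers outcomes 1 and 2 and average DALY (Section 4.6), because outcomes 3 and 4 have no raw Note A score.

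CHEW effects and the full vital-sign list are not needed. MO-rated severity should stay out unless it is recorded before Note A is read, which the SAP does not state.

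The cost is a few lines of SAP text and about six model terms if there are four MOs. Demographics are in the EMR by Section 2.2. MO identity is not listed there, so its availability should be confirmed. Section 5.4 says the data have not yet been analysed by treatment status, so the change can still be prespecified.

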5.2 Data Quality Indicators

Quality of MOs. We will construct objective treatment and testing decision quality indicators for MOs in an analogous way to the measures in sections 3.5 and 4.4 based on the screening test results.

We will also report the share of cases in which MOs update their own treatment plan after reviewing SOAP Note A, SOAP Note B, and the screening test results.

Finally, we will report the assessment of error in the MO’s SOAP note by the MDs.

Quality of DALY measures. We will verify the direction of DALY rating change between Note A and B with the response to the question

All things considered, do you prefer the treatment plan in SOAP Note A or in SOAP Note B?

As a secondary outcome, we will make a scatterplot of QALY loss against whether the MO classifies a patient as mild, moderate, severe, pooling both notes. What we expect to see is that the scope for QALY losses generally occur in the most severe patients.

More generally, we will analyze the response of the DALY ratings of MOs and MDs to subjective and objective indicators of error: indicators for deviations from the MO’s SOAP and types of harm incurred (section 2.3.1) and objective treatment misallocation (3.5).

We will also analyze the agreement between MO and MD DALY ratings relative to the agreement on the various harm measures between the three MDs.

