Statistical Analysis Plan; Can Feedback from a Large Language Model Improve Health Care Quality?

[name]*, [name]† [name]‡ [name]§ [name]¶

April 29, 2025

1 Introduction

The quality of healthcare in low- and middle-income countries is notoriously low (Banerjee et al., 2023). In Nigeria, only a small proportion of primary care patients are seen by a Medical Officer instead of a mid-level provider such as a Community Health Extension Worker or Community Health Officer. Access to qualified medical doctors is a barrier to good health care (Okeke, 2023).

This project tests whether Large Language Models (LLMs) can improve patient care in Nigerian primary care clinics by giving customized and instant feedback to the provider in natural language. An LLM-based tool integrated into an electronic patient record management system provides “second opinions” to community health extension workers (CHEWs) at two clinics in Nigeria. These second opinions are intended to mirror what a reviewing physician might advise the CHEWs after seeing or hearing their initial report on a patient.

2 Experimental Design

For our main analysis, we use a within-patient comparison of two patient notes created by the CHEW; one during the initial patient consultation, and one after the LLM feedback was received. The patient is also seen by a fully trained medical officer who is in charge of patient care. The MO conducts a blinded review of the CHEW’s patient notes to measures changes in the CHEW’s care as a result of the LLM feedback. Our data comes from the information captured in the electronic medical record (EMR) of the patient and from survey data collected from CHEWs, reviewing MOs, and a panel of reviewing Medical Doctors (see below).

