2.5 MD Panel

A panel of three Medical Doctors (MDs) will review the patient data (CHEW notes, MO notes, and LLM feedback).

Flagging MO error. In a first step, they will review the MO notes only and record whether there is any error in the diagnosis or treatment proposed in the conditional note or in the final note. If an error is identified the MDs will rate the error by severity to distinguish medical mistakes from differences in opinion about a patient who is not present.

SOAP note rating. Next, the MDs will carry out an independent evaluation of the assisted and unassisted SOAP notes as described in the sections “Types of harm incurred” and ”“Measuring Healthy Time Lost” (section 2.3.1 above).

LLM review. Finally, the MDs will also review the LLM feedback and answer the following questions:

“Did the CHEW follow all, some, or none of the LLM recommendations?”

If some or none: "Imagine the CHEW had followed all the recommendations of the LLM. Would the resulting treatment plan be an improvement over their assisted note?" (Yes/no)

If yes: "Please explain."

“Did the LLM make any mistakes?” (Yes/no)

If yes: "Was any aspect of the CHEW's assisted treatment plan worse than the unassisted plan because the CHEW followed the LLM's erroneous recommendation?"

If yes: "Please explain."

3 Primary Outcomes

Our study will have four primary outcomes, each assessing differences between the CHEW's assisted and unassisted note.

1. An indicator for an error in the treatment plan in the SOAP note (with the potential for harm)
2. An indicator for an error in the treatment plan that causes a loss of at least X quality-adjusted life days (where X is the highest benchmark on the appropriate DALY scale so that at least 5% of patients have an error that large in the unassisted SOAP note)
3. An indicator for the better treatment plan

4. Consistency of treatment with the “standard of care” based on our screening tests and medical guidelines.

We describe the construction of each metric in detail below.

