4.6 Average and Distribution of DALY lost

We use our DALY measure of harm indirectly in several primary outcomes (probability of error and severe error, which note is the better note). As a secondary outcome, we will measure the effect of LLM assistance on average DALY (this is not our primary outcome because we are concerned about power being limited due to a few outliers).

Additionally, we will show the full distribution of DALY ratings for the assisted and unassisted notes.

4.7 3rd Party MD Review of CHEW notes and MO notes

We will reassess our primary outcomes using the MD DALY ratings and subjective harm measures (section 2.5).

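### The rater-agreement check in SAP 5.2 should also cover the within-patient note difference, because agreement on DALY levels says little about which note raters think is better

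*SAP*

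**What the plan says.** SAP 5.2 (Quality of DALY measures) plans to study "agreement between MO and MD DALY ratings relative to the agreement on the various harm measures between the three MDs". It names no agreement statistic. Under 2.3.1 the MO gives one healthy-time-lost rating per SOAP note. Under 2.5 "the MDs will carry out an independent evaluation of the assisted and unassisted SOAP notes", covering both types of harm and healthy time lost, so note differences and MD-MD agreement on DALY can be computed from planned data.

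5.2 has a separate phrase for the contrast: "We will verify the direction of DALY rating change between Note A and B". That check compares the rating change with the answer to the A/B preference question, not the MO with an MD.

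The main analysis rests on the contrast. Section 2 says "we use a within-patient comparison of two patient notes created by the CHEW", and in the model of 3.1 "a_i is a patient (patient-test) fixed effect". Under 3.4 the better-plan indicator depends on which note has the lower DALY loss. Section 4.6 adds the effect on mean DALY, and 4.7 repeats the primary outcomes with the MDs' ratings.

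**The concern.** A rating mixes two things: how much harm is possible in this patient, and how good this note is. The SAP expects the first to vary widely. The scale runs from 0 minutes to 23 years (28 for children), 3.3 expects heavy skew and many zeros, and 4.3 expects the scope for loss to depend on severity of illness. Two raters who see the same patient share most of that variation, and a correlation or ICC of the ratings will reflect it. The patient fixed effect then removes it from the treatment comparison.

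So a high figure from 5.2 could be taken as support for the better-plan outcome and the DALY effect when it carries little information on either.

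The comparator adds a second difficulty. If the harm measures on which MDs are compared exclude DALY, rater pair and measure change together, and a low MO-MD figure could not be assigned to the rater or to the scale.

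**Working it through.** The SAP gives no agreement statistic, target or figure, so there is nothing to reproduce. The variance components below are assumptions, shown over a range.

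**Model.** Rating (log harm) = patient component shared by both raters + note component. Let s be the between-patient share of variance and ρ the correlation of the note components between raters. Then

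- correlation of levels = s + (1 − s)ρ
- correlation of A-B differences = ρ

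**Raters unrelated on the notes (ρ = 0), note SD 0.5, variance 0.25**

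| Patient SD | Level correlation | Difference correlation | Same direction |
|---|---|---|---|
| 1.0 | 1/1.25 = 0.80 | 0 | 50% |
| 1.5 | 2.25/2.50 = 0.90 | 0 | 50% |
| 2.0 | 4/4.25 = 0.94 | 0 | 50% |

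**Dependence on s.** Simulation with 500 patients and two notes each agrees with the formula. At ρ = 0 the level ICC is 0.30, 0.50, 0.70, 0.80 and 0.90 for s = 0.3, 0.5, 0.7, 0.8 and 0.9. At ρ = −1, where raters reverse the order in every patient, it is 0.8 − 0.2 = 0.60 at s = 0.8 and 0.9 − 0.1 = 0.80 at s = 0.9. At small s the effect fades.

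**Shared zeros.** With 30% to 50% of patients rated zero by both raters (patient SD 1.5, note SD 0.7), the rank correlation of levels is 0.93 to 0.97 and of differences 0.

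**Adult benchmarks (Appendix C), assumed bin mix.** Each rater uses the patient's underlying severity bin in 60% to 100% of cases and otherwise an adjacent one; position within the bin is independent. Rank correlation of levels is 0.83 to 0.96. Rank correlation of differences is about 0, with about 50% agreement in direction.

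**Hand check.** Six patients, twelve ratings, each patient's two ratings adjacent in rank, and the second rater swaps them in every patient. Each rank moves by 1, so Σd² = 12 and Spearman = 1 − 6·12/(12·143) = 0.96, with 0% agreement on the better note.

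**Ties also affect the better/same/worse call.** Let z be the share rated the same by both raters, with direction at chance otherwise. Observed agreement is z + (1 − z)/2 and expected agreement z² + (1 − z)²/2.

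- z = 0.3: (0.65 − 0.335)/(1 − 0.335) gives kappa 0.47.
- z = 0.5: (0.75 − 0.375)/(1 − 0.375) gives kappa 0.60.

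Among the remaining pairs, agreement in direction is 50% and kappa is 0. Chance correction over all pairs is therefore not enough.

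**The case against.** Several points on the other side stand.

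- Levels matter in this trial. The severe-error indicator in 3.3 is a threshold on the level, 4.6 displays the whole distribution, and the raw-score check in 5.1 drops the patient fixed effect. A reader might infer that DALY ratings enter only through the note contrast, or that level agreement is worthless. The SAP supports neither.
- Agreement on levels is an inference, though the natural one given the separate wording for the rating change. With no statistic named, part of the fault is under-specification.
- The comparator may be sound. Section 4.6 itself treats DALY as a measure of harm, so the phrase can include MD-MD DALY agreement. Against that, 4.7 lists DALY ratings and subjective harm measures separately. The text leaves it open.
- The estimand is an average. If a common assisted-note benefit of 0.3 log units is added to the model with ρ = 0, both raters recover −0.30 although their differences are uncorrelated. Poor agreement on the contrast would not by itself invalidate the average effect, and 4.7 tests whether independent raters reproduce it. But 4.7 compares averages only: equal averages can come from different patients.
- 5.2 also checks direction against stated preference and relates DALY ratings to error indicators. Neither sets MO against MD on the same patient's pair of notes.
- ρ = 0 is imposed, so the figures show what can happen and do not predict it.

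**Conclusion.** The point holds as a cheap improvement to a validation analysis. As worded, 5.2 can return high agreement between raters who agree only by chance on the better note. The size (level correlation 0.80 to 0.94 against a difference correlation of 0) rests on assumed variance components and independent note components. A large between-patient share is plausible on the SAP's own expectations, but the SAP does not give it; at a share of 0.3 the level ICC is only 0.30.

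A reader might go further and infer that the primary results are unreliable or that the MO's ratings cannot be trusted. The document does not support that: no primary estimate, threshold or decision rule depends on this check.

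**What to change.** Keep level agreement in 5.2 and add wording to this effect:

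- MO-MD agreement will also be computed on the within-patient A-B difference in DALY loss (rank correlation) and on the better/same/worse call derived from it.
- The main figure for each will be taken among pairs where at least one of the two raters sees a difference; the figure over all pairs will be given beside it. Patients for whom the MO reports no meaningful difference under 3.4 count as the same for the MO.
- Name the statistic for each measure, and report MO-MD and MD-MD agreement side by side on the same measure, DALY included.

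The restricted set is chosen by the ratings and leaves out pairs that both raters tie, which pulls kappa down. The MO-MD figure is therefore best read against the MD-MD figure computed the same way.

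The cost is a few lines of SAP text and no new data. The downside is that the agreement figures will probably look less favourable.
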